- 3. How does peers' experience influence the relationship between price, on the one hand, and perceptions, technology adoption and use outcomes, on the other? Do peer effects increase or decrease the price elasticity of demand for the new technology?
- 4. How do perceptions of a technology change over time among households that adopt that technology initially? How do these perceptions relate to objective measures of stove performance (e.g., personal exposure to pollutants), and what is the relationship between perceptions and technology *use* over time?

II. BACKGROUND AND SIGNIFICANCE

[figure not shown]
Technology adoption continues be a central research topic in microeconomics because of its importance in understanding economic development and because of the kaleidoscope of models explaining different economic, psychological, and sociological factors at play. Two key strands of literature examine the roles of prices and peer effects on technology adoption.

Prices and technology adoption and use

Setting subsidy and end-user price levels for a new technology reflects a fundamental tension between rapid diffusion and sustainability (Mobarak et al. 2012; Dupas 2014). On the one hand, subsidizing adoption of socially beneficial technologies may be necessary to promote widespread adoption, at least in the short-run. Indeed, recent evidence has shown very high, and even discontinuous, price elasticities of demand for a number of low-cost health technologies in developing countries: new technologies offered at a positive price tend to exhibit much lower demand than identical products offered for free. The most recent World Development Report (World Bank 2015, see Figure 1) details numerous examples of this phenomenon. In one example that is particularly relevant for this proposal, Mobarak and coauthors (2012) analyze a field experiment with the distribution of cookstoves in Bangladesh. The researchers find demand for these modern stoves to be extremely price elastic, with only 5% of households purchasing the stoves with no discount and a 50% discount yielding 8-12% higher demand (relative to the full cost treatment).

On the other hand, many argue that goods given away for free or at low cost will be *used* at lower rates than goods for which users pay higher prices. There are at least two theoretical foundations for this hypothesis. First, price-based incentives for new technologies (or any scarce good) ensure allocation of

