Since some households will be offered stoves for free while others will be offered stoves at positive prices, the benefits will be *unequal* across participants. However, these prices will be varied *at random*, such that the benefits will not be *inequitable*: at the outset of the study, all respondents will have an equal chance of being assigned to different price levels. This study design will be clearly explained to participants at the outset, as described in the Recruitment section (VIII) and specified in the Consent Form. Randomization of clusters to different price levels will be done in a participatory and transparent manner – for example, we may conduct the randomization during a meeting involving representatives from the different clusters, allowing these individuals to draw numbers out of a hat to determine their clusters' stove price levels, and videotaping this process so that it is available to show respondents concerned about the fairness of the price assignment.

Analysis of Key Research Questions and Power Calculations

Econometric analysis of data from the experiments will estimate regression models for three key outcome variables: stove adoption, use, and perceptions of quality (pre- and post-adoption). Multiple indicators of each of these outcomes will be possible. For example, adoption measures can include binary indicators for purchase / receipt of *any* stove, as well as indicators for the number and type(s) of stoves selected. Stove use measures will come from surveys and electronic monitors, and can be specified at the stove or household level over various time periods (e.g., reported use on previous day from survey vs number of uses over a month from SUMs). Perceptions measures can include overall favorable / unfavorable ratings as well as more continuous measures from Likert-scale and/or subjective expectation responses.

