Instrument-based measurements												
Data analysis												
Dissemination												
- Preparation of reports and peer-												
reviewed publications												
- Presentation at scientific												
conferences												
- Workshop in study area												

V. FUNDING

This research is being funded by the National Science Foundation's Economics program and the National Institutes of Health's Clean Cooking Implementation Science Network.

VI. ABOUT THE SUBJECTS

Component #1: P3 Bio

As shown in Figure 5, a total of 300 households will be enrolled in the P3 Bio component of the study. In each household, the primary cook (typically female, aged 18-55 years old) will serve as the main study participant. In households where another male household member makes financial decisions, we will conduct a secondary survey with this individual as well. We anticipate that all of these households will complete the study. The study population includes two main ethnic groups: Kasem and Nankam. The population will be split roughly evenly between these two groups.

Table 3: Subject Populations

Subject Population(s)	Number to be enrolled in each group
Group S1: Rural households from the same	150 households
clusters as REACCTING study households	

Group S2: Rural households from different150 householdsclusters from REACCTING study households150 households

Inclusion / Exclusion Criteria

Sample selection will proceed in two phases. First, clusters will be selected for inclusion in the study. All of the 25 REACCTING study clusters will be included to form the S1 group clusters. GIS mapping will then be used to *exclude* clusters that are close to those S1 clusters (using a buffer distance determined using preliminary data on social ties), and 25 S2 group clusters will then be randomly selected from the remaining clusters.

Second, the required number of households will be selected from each cluster. We will use the same inclusion and exclusion criteria used to select households in the existing REACCTING study. Using data from the district's demographic surveillance survey, a sample frame of eligible households will be created using the following inclusion criteria:

- Classified as "rural"
- Uses biofuel as main cooking fuel source
- Has woman in household aged 18-55 and at least one child under five (since women and children are the most vulnerable to cookstove smoke)

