For the LPG supply survey, NHRC interviewers will visit each business, ask to speak to the owner or manager, and explain the purpose of the survey. These individuals will then be read the informed consent statement, and will indicate whether they agree to participate in the survey.

IX. COMPENSATION

Small in-kind tokens of appreciation are offered to study participants as compensation. These include items such as bags of rice, bars of soap, or cell phone credits. As with all aspects of the field work, we defer to our local collaborators for guidance on appropriate, non-coercive methods of compensation for study participants.

X. CONSENT PROCESS

Informed consent will be obtained for all study participants at the outset of this study. Given that the study poses minimal risks to participants, oral consent will be obtained. The enclosed consent statement describes the purpose of the research and the research design, including the design of the experimental manipulations of price and peer effects, and each of the data collection activities, including the purpose of the data collection, what will be required of the participant, and any anticipated risks and/or benefits. After each consent statement is read, the participant will be asked whether or not they agree to participate in that data collection activity, and the response will be recorded by the data collector. Participants will be assured that they may decline participation in certain data collection activities, specifically photographic monitoring for a 48 hour period, while still agreeing to participate in all other study activities. All participants will be given contact information for the study personnel. Consent will be sought before pictures of participants are added in reports and publications.

Consent statements, along with surveys and other materials, will be translated into the two local languages (Kasem and Nankam). For some urban households and LPG supply surveys, some participants are likely to opt to take the survey in English. Following NHRC practices, translations are done orally and are developed and agreed upon by interviewers prior to the inception of the surveys. These translations are typically not written down.

XI. PROCESS TO DOCUMENT CONSENT IN WRITING

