Survey Data	Household-level social network, perception, behavioral, health,	ArcGIS, CSV, DTA (Stata)	Units, lat/lon of compounds/ houses	Team access only to full dataset with identifiers / De- identified data open access with	Non- commercial use only	CU password protected computer

	demographic, and socioeconomic data			registration / statement of interest		
Stove Use Data	Time series measurements of stove temperature	ASCII, CSV, EXCEL, MAT (Matlab)	Units, variables (compounds, stove type) methods, uncertainty	Open access with registration/ statement of interest	Non- commercial Use Only	CU password protected computer and servers
Personal Exposure, Proximity, and Air Quality Data	48 hr real-time personal CO data; 48-hr integrated personal PM _{2.5} samples; time series of individual proximity to stoves/sources; household environment CO, CO ₂ , and PM _{2.5} samples (NO and VOCs in subgroup)	CSV, TXT, EXCEL, MAT, (Matlab)	Units, variables, (Lat/lon of measurements, characteristics) methods, uncertainty and calibrations	Team access only to full dataset with identifiers / De- identified data open access with registration / statement of interest	Non- commercial use only	CU password protected computer and servers
Short Term Stove Use and Proximity Data	48 hours of 30- second-interval photographs	JPG	Timestamp, Date, Temperature	Team access only to full dataset with identifiers/ De- identified data open access with registration / statement of interest	Non- commercial use only	CU password protected computer and servers

Types of data

The raw data generated by the proposed research includes (a) quantitative social survey data and analyses; (b) time series measurements of stove temperature from the Stove Use Monitors (SUMs), and (c) personal exposure, proximity to stoves, and microenvironmental (near-stove) air quality data. Surveys will be conducted using paper hard copies generated using the Remark Office OMR software, a "scantron" like format that allows responses on subsequent .pdf files to be read in to Excel files automatically. Air quality data will be collected from the instruments in the field in the form of raw sensor signals, typically voltages, with time stamps. In addition to this field data, we will also be routinely compiling calibration data for each sensor. This calibration data will be in the same format as the field data.

Data Storage and Archival

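### The agreed Kasem and Nankam wording of the repeated perception items is typically not recorded, so wording drift between rounds could not be told apart from a change in perceptions

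*Combined protocol and SAP*

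**What the plan says.** Section X (Consent Process) provides for consent statements, surveys and other materials to be rendered in Kasem and Nankam. On method it says that "translations are done orally and are developed and agreed upon by interviewers prior to the inception of the surveys", and then: "These translations are typically not written down".

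The source instrument is fixed on paper. Section XIV (Types of data) says: "Surveys will be conducted using paper hard copies generated using the Remark Office OMR software". Section XVII adds that interviewers are trained in survey administration.

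Section IV (Analysis of Key Research Questions and Power Calculations) makes perceived quality, before and after adoption, one of three key outcomes. On its measurement: "Perceptions measures can include overall favorable / unfavorable ratings as well as more continuous measures from Likert-scale and/or subjective expectation responses". Table 1 there powers two contrasts on a 0-100 Likert index with an SD of 25.

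Section XII has the full baseline survey repeated at the end of the study, with follow-up on perceptions in between. Research question 4 in section I asks: "How do perceptions of a technology change over time among households that adopt that technology initially".

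For P3 Bio, section VI says: "The study population includes two main ethnic groups: Kasem and Nankam", in roughly equal shares.

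**The concern.** Research question 4 is a before-after comparison among adopters. It assumes that an item means the same thing at each round. The printed form fixes the source text, but a Kasem or Nankam speaker responds to the spoken rendering. That rendering is agreed once, before the surveys begin, and then typically kept only in interviewers' memories. The documents describe no fixed local-language text, no back-translation and no re-agreement before later rounds.

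If the rendering of a Likert or expectation item shifts between baseline and endline, the shift is added in full to the estimated change. Randomization does not remove it, because the comparison is over time and not between randomized groups. Without a record, nobody could later show whether it happened.

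There is a lesser effect on the peer (S1 v S2) and price contrasts. If the two languages render an item differently, an unequal language mix between the compared clusters adds error to perceived quality.

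**Working it through.** **Inputs from the documents.** Index SD 25. Peer contrast: 10 points, 147 v 147. Price contrast: 10 points, 84 (P1) v 70 (P0). 25 clusters each in S1 and S2. Two groups of roughly equal share.

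**Inputs assumed.** The documents give no size for a wording shift, so a range is shown. Also assumed: within-person correlation r between rounds of 0 to 0.5; n = 147 for the change analysis (the number of adopters is not known in advance); one language per cluster; half the clusters speaking each language; 7 households per cluster for the price contrast, which gives 10 v 12 clusters.

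**Table 1 first.** The standard errors are
- peers: 25 × √(2/147) = 2.92
- price: 25 × √(1/70 + 1/84) = 4.05

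A one-sided 5% test then gives power 0.963 (stated 0.96) and 0.796 (stated 0.800). A two-sided test gives 0.929 and 0.696 and matches neither. Table 1 states neither alpha nor sidedness. These figures do not depend on translation; the check only confirms the SD and the standard errors used below.

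**Change between rounds.** For a shift δ common to all respondents and no true change:
- SE = 25 × √(2(1 − r)/147), which is 2.92 at r = 0 and 2.06 at r = 0.5
- P(reject) = Φ(δ/SE − 1.96) + Φ(−δ/SE − 1.96)

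| δ (points) | r = 0 | r = 0.5 |
|---|---|---|
| 2 | 0.105 | 0.163 |
| 5 | 0.403 | 0.679 |

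The bias is δ itself whatever n is. The rejection rate depends on n: at n = 294 it is 0.163-0.279 for 2 points and 0.679-0.929 for 5 points.

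**Peer and price contrasts.** For a fixed gap g between the two languages, the chance difference in language share has SD √(0.25/a + 0.25/b) for a v b clusters:
- peers, 25 v 25: 0.141
- price, 10 v 12: 0.214

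The added error has mean zero and SD g times that value. Combined SE = √(SE² + added SD²):

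| Contrast | g | Added SD | SE before | SE after | Increase |
|---|---|---|---|---|---|
| Peers | 5 | 0.71 | 2.92 | 3.00 | 3% |
| Peers | 10 | 1.41 | 2.92 | 3.24 | 11% |
| Price | 5 | 1.07 | 4.05 | 4.19 | 3% |
| Price | 10 | 2.14 | 4.05 | 4.58 | 13% |

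If an analysis ignored this error, a nominal 5% test would run at 5.7-7.8% (peers) and 5.8-8.3% (price). Section VI implies 6 households per cluster (150/25), not 7. The price imbalance SD is then 0.5 × √(6/70 + 6/84) = 0.198, slightly smaller, and the conclusion is the same. The starting standard errors treat households as independent, as reproducing Table 1 requires. Allowing for clustering would raise them and make the relative increases smaller.

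**The case against.** The strongest reply is that the plan does have safeguards. The rendering is agreed among interviewers before fieldwork, all work from one printed form, the endline repeats the baseline content, and interviewers are trained. The text says typically, so some wording may be written down. All of this stands. A reader might infer that nothing holds the wording together; that goes too far. What the safeguards lack is a record that carries the agreed wording forward and lets anyone check it.

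A second reply is that randomization protects the main contrasts. This also stands. The R clusters were randomly selected, the S2 clusters will be, and prices are randomized by cluster and balanced across S1 and S2. A reader might infer a directional bias in the peer or price effects. The documents do not support that: it would need languages or interviewers to be unevenly spread over the groups, which they neither indicate nor rule out. A drift common to all groups would also cancel from a comparison of changes between price groups, though not from the change itself.

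A reader might also infer that the P3 Gas auction explanation is translated from memory. Section X does not name it. Section XII has project staff explain it at home with two practice rounds, without describing a script or language, and section VI says the urban sample mostly belongs to one of the two groups. At most it falls under other materials.

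One could argue that interviewer differences double the variance of an area mean: with an assumed interviewer SD of 5 and 30 households each, 1 + 29 × 0.038 = 2.1. No planned contrast compares areas, so this is not evidence about the study's estimates.

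Finally, the survey forms are not among the documents, so they may already carry language and interviewer fields. Section IV lists no covariates for any model, so the absence of these two is not a specific omission.

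**Conclusion.** The point holds for the repeated perception items and research question 4, and it is minor. The mechanism follows from the stated procedure: a between-round shift biases the estimated change by its full size and leaves no trace. Whether any shift will occur, and how large, is unknown. The false-rejection rates of about 11-16% (2 points) and 40-68% (5 points) show sensitivity under assumed shifts; they do not predict error rates.

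For the peer and price effects on perceptions, the consequence is limited to extra cluster-level noise of roughly 3% to 13% on the standard error for assumed language gaps of 5 to 10 points, provided languages and interviewers are not confounded with group. Adoption rests on signed or thumbprinted agreements, and monitored use on temperature sensors, so neither depends on item wording. Reported use does.

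**What to change.** In section X, replace the statement that translations are typically unwritten with a requirement covering the perception, expectation and reported-use items:

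- Write down or audio-record the agreed Kasem and Nankam wording before the first round, and use it unchanged in all rounds.
- Record survey language and an interviewer code on each form, if the forms do not already do so.
- In section IV, add a sensitivity analysis of the perception models that adjusts for language and interviewer.

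The first step is the one that protects research question 4. Covariates cannot remove a shift common to everyone at a given round, because it coincides with time; they help only with differences between languages or interviewers.

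This version is dated January 2018, in the third year of the timeline, so early rounds may be complete. If so, start from the next remaining round, recover language and interviewer from field records where possible, and report the unrecorded baseline wording as a limitation on the before-after results.

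Putting the auction explanation under the same fixed wording is a sensible extension, not the repair of a documented fault.

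The cost is a few days of existing interviewer training time, two form fields and two covariates, with no extra participants or visits.

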- 4) Short term stove use and proximity monitoring: In a subset of the households participating in personal exposure measurements, we will collect validation data for when stoves are being used and when participants are near these stoves. Obtaining this data will be accomplished through taking photographs in intervals (either every 30 or 60 seconds) of the two main cooking areas in a household over a 48-hour period. The equipment used will be two wildlife cameras equipped with infrared LEDs for night vision and timestamp capabilities placed on a tripod approximately 10 feet away from the two main cooking areas. The night vision should be of no concern for participants as this feature uses dim red lights that are minimally visible. Photographs will be collected for 48 hours. The field team will record which stoves are monitored so that during image processing a record can be made for each timestamp of (1) Are any of the cookstoves in this cooking area considered 'on' at this time? and (2) Is the primary cook visible near this cooking area and are they wearing the personal exposure equipment? After taking note of every time the primary cook is wearing the personal exposure equipment in the frame and which stoves are lit at which times, all images will be deleted. All that will remain is a database of stove 'on' times that will be compared to temperature data from corresponding stove use monitors and participant 'nearby' cooking area times that will be compared to proximity data.

Following their recruitment into the study by interviewers at the time of the baseline survey, households will be instructed to attend a stove demonstration meeting at a location near their house (in their cluster). Interviewers will provide information on the time, date, and location of these meetings. At the meeting, the stove and fuel options will be presented and demonstrated to participants. As noted above, the P3 Bio intervention will use two stoves similar to the REACCTING stoves (Greenway Jumbo and ACE1). The market value of the Greenway stove is about \$30, and the ACE (including a small solar panel and light)

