- Household survey poses minimal risks to participants: To the extent that any information is sensitive, the steps described in Part XX will ensure that the data is not made publicly available in a way that could link responses to any individual participant. Interviewers will be trained in proper survey administration techniques and attitudes to ensure data quality and avoid social desirability bias (particularly relating to use of and attitudes toward the new stoves).
- Stove use monitoring: Participants will be informed of the risk of malfunctioning equipment and a protocol will be established for contacting study personnel if any of the equipment appears to be malfunctioning. Confidentiality of stove use data will be maintained – in particular, interviewers will not have access to this data when administering household surveys (which also ask about stove use) so that interviewers can ask questions without the respondent feeling like they are being given a "test" with right and wrong answers.
- Personal exposure measurements: As above, participants will be advised to be on the lookout for the small risks of malfunctioning equipment.
- Short term stove use and proximity measurements: The risks to participants' privacy from the
 photographic data will be addressed by only allowing team members to view these photos for the
 purposes of coding stove use and participant location, and deleting all photographs immediately
 after image processing, which will be done as soon after data collection as possible. Participants
 and those in the area will also be informed of the photographs before data collection begins, so
 those around have the opportunity to change any personal behaviors they do not wish to be seen
 on camera. Participants may continue any activities they are comfortable with.

XVIII. POTENTIAL BENEFITS

There are several potential benefits to participants. All households will have a possibility of receiving new stoves. This new technology has potential time and fuel savings as well as possible health benefits for participants.

Household members will also be involved in the research process throughout the study. We will fully inform participants about the instruments we are using and the objectives of the research, and will be open to suggestions about ways to improve our research methodology or measurement routines. We may also enlist households' participation in disseminating our results to the broader community.

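### The photo-coding rule joins the cook's presence and equipment wear in one condition before the images are deleted, so the proximity reference mixes the two

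*Combined protocol and SAP*

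**What the plan says.** Section XII, item 4 (short term stove use and proximity monitoring) describes interval photographs of a household's two main cooking areas over 48 hours. They are taken in a subset of the households that have personal exposure measurements. The stated purpose is: "we will collect validation data for when stoves are being used and when participants are near these stoves".

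For each timestamp the coder answers two questions.

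- The stove question begins "Are any of the cookstoves in this cooking area considered" and asks whether they are on at that time.
- The cook question is "Is the primary cook visible near this cooking area and are they wearing the personal exposure equipment".

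The following sentence says what is noted before the photographs go: "every time the primary cook is wearing the personal exposure equipment in the frame", and also "which stoves are lit at which times, all images will be deleted". The same item states: "The field team will record which stoves are monitored". Two things remain in the database. Stove on times are to be set against temperature data from the corresponding stove monitors, and times when the participant was nearby are to be set against proximity data.

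Section XVII (Management of Risks) repeats the privacy safeguard as "deleting all photographs immediately" after image processing. Table 6 in Section XIV, however, lists 48 hours of 30-"second-interval photographs" in JPG format as a data type of its own, with access rules that include open access to a de-identified version, and with an archive location.

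**The concern.** The photographs serve as the reference standard for the proximity data, so the reference should say whether the cook was near the stove. As worded, it says whether she was near the stove and also wearing the equipment. Three states of the cook (present and wearing, present and not wearing, absent) collapse into two codes, and the middle state falls in with absence. Once the images are deleted it cannot be separated out again.

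Two uses of the data depend on that middle state. A test of how well the proximity device works while worn needs the unworn times removed, not counted as the cook being away. A statement of how much time cooks spend at the fire without the sampler needs those times counted. Personal exposure is the objective measure named in research question 4, and Section XIX rests its interim safety check on it. The equipment is worn for 48 hours and may include a pump carried at the waist (Section XII, item 3), so some removal is plausible. The photographs are the only objective check on wear that the document describes.

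**Working it through.** The plan gives no sample size, error rate or target precision for this validation, so there is no stated figure to reproduce. The check compares the sentences and then asks what the stored data can identify.

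**1. Volume of data (inputs from Section XII, items 2 and 4).**
- Photographs per camera over 48 hours: 48 × 3,600 / 30 = 5,760, or 48 × 3,600 / 60 = 2,880.
- Readings per stove monitor at 5-minute spacing: 48 × 60 / 5 = 576.
- That is 10 or 5 photographs per monitor reading. The photographs are frequent enough; the weakness lies in what is coded from them.

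**2. What the cook code stores.**

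| State of the cook | Code on the natural reading |
|---|---|
| Visible near the area, equipment worn | yes |
| Visible near the area, equipment not worn | no |
| Not visible near the area | no |

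The recorded share of yes codes is q = P(near) × P(wear | near). One observed number cannot determine two unknowns. With an assumed q of 0.10, P(near) = q / P(wear | near):

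| Assumed P(wear given near) | Implied P(near) |
|---|---|
| 1.00 | 0.10 / 1.00 = 0.100 |
| 0.75 | 0.10 / 0.75 = 0.133 |
| 0.50 | 0.10 / 0.50 = 0.200 |

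The same database fits all three rows.

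**3. Direction of the error.** The document does not state the type of proximity device. Assume that it is worn with the exposure equipment and is faultless while worn. Per 1,000 timestamps with q = 0.10 and half wear, 100 are present and worn, 100 present and unworn, and 800 absent.

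- *Unworn device left away from the fire.* It reads not near in the 100 unworn timestamps, and the merged code is also no, so every timestamp agrees. Against presence alone, the device detects 100 / 200 = 50%.
- *Unworn device left beside the fire.* It reads near in those 100 timestamps while the merged code is no. The device is charged with 100 false positives among 900 no codes, so apparent specificity is 800 / 900 = 88.9%, although the cook was in fact there.

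The first case hides failure and the second creates it. The text does not say which would occur.

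**4. The stove question.** With two stoves in an area there are four states: neither lit, first only, second only, both. An any-stove-on code gives the same value to the last three. A record of which stoves are lit at which times separates all four. The planned comparison is with each stove's own monitor (item 2 has monitors on all stoves in the household), so only the second form supports it directly. An area with a single stove raises no difficulty under either form.

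**The case against.** The strongest reply is that wear was never a validation target. The purpose sentence names stove use and proximity, and Section XVII says that staff view the photographs to code stove use and participant location. The retained variable is described as nearby times, which could mean presence alone. The compound question has two halves, and nothing forbids entering them separately. If the proximity device is worn, limiting the reference to worn time is also a defensible way to test the sensor, since an unworn device cannot locate the cook.

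Part of this stands. The merged code is the natural reading, not a certain one. But no sentence tells the coder to keep the halves apart, and the only sentence on what is noted about the cook names the joint event. If nearby does mean presence alone, that sentence disagrees with it and still needs correction. A worn-only test is legitimate, but it requires the unworn times to be excluded; coding them as not near does the opposite.

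A reader might infer three stronger things.

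- *That stove-level monitor accuracy is lost.* It is not, if the later sentence is followed: it records which stoves are lit and when, and the field team records which stoves are monitored. What remains is a mismatch in wording with the any-stove question.
- *That proximity accuracy is overstated.* Step 3 shows that the error can go either way.
- *That the trial's main results are at risk.* The cameras cover a subset of a subset, and no described analysis uses the photographs to adjust exposure or stove use. Stove monitors measure use; adoption is defined in Section IV by purchase or receipt.

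**Conclusion.** The point holds for the coding of the cook. On its natural reading, Section XII, item 4 stores a cook who is present without the equipment as if she were absent, and deletion makes this permanent. The proximity reference then identifies only P(near) × P(wear | near). Unworn time can be neither set aside in the validation nor reported as wear compliance.

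The size cannot be stated from the document, which gives no wear rate, time near the stove or type of proximity device. The values of q and of wear above are assumptions that show what is not identifiable; they do not estimate what will happen. The direction of the error is open. The consequence is confined to the validation substudy and does not reach the price or peer comparisons.

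Two smaller inconsistencies stand beside it. The any-stove question and the which-stoves sentence are at different levels. Table 6 gives access and archive entries for photographs that Sections XII and XVII say will be deleted. The table may simply be listing the raw format, but its archive entry still conflicts with the safeguard offered for privacy.

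**What to change.** Replace the two coding questions with separate fields for each timestamp:

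- for each stove ID: on, off or not visible;
- primary cook visible near the area: yes or no;
- if visible, exposure equipment worn: yes, no or cannot tell.

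Validate the proximity data against cook visible, and add an analysis restricted to timestamps with the equipment worn, so that device accuracy and wear are not confused. Report the worn share of cook-visible time as wear compliance. Reword the sentence on what is noted before deletion to match these fields, and delete images only once the fields are complete.

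In Table 6, list the coded dataset in place of the JPG photographs, so that the access and archive entries agree with the deletion promise.

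The cost is a revised coding sheet, one changed table row and slightly longer coding, mainly where an area has several stoves. The photographs, the coders and the deletion promise stay as they are. The change has to be made before images are coded and deleted.
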